**Figure 2 Management of Hypertension**

BP = blood pressure, HTN = hypertension, Tx = treatment.

#### 8.4.1.1.3 MANAGEMENT OF POSTERIOR REVERSIBLE LEUKOENCEPHALOPATHY SYNDROME/REVERSIBLE POSTERIOR LEUKOENCEPHALOPATHY SYNDROME

Posterior Reversible Leukoencephalopathy Syndrome (PRES)/Reversible Posterior Leukoencephalopathy Syndrome (RPLS) is a neurological disorder that can present with headache, seizure, lethargy, confusion, altered mental function, blindness, and other visual or neurological disturbances. Mild to severe hypertension may be present. An MRI is

necessary to confirm the diagnosis of PRES/RPLS. Appropriate measures should be taken to control BP (see [Section 8.4.1.1.1](#) and [8.4.1.1.2](#)), and neurologic consultation is advised. In subjects with signs or symptoms of PRES/RPLS, dose modification guidelines as per [Table 1](#) should be followed.

#### 8.4.1.1.4 MANAGEMENT OF PROTEINURIA

Regular assessment for proteinuria should be conducted as detailed in the Schedule of Assessments ([Table 5](#) and [Table 6](#)). Guidelines for assessment and management of proteinuria are summarized as follows:

##### Grading of Proteinuria

- Grading according to CTCAE 5.0 ([Cancer Therapy Evaluation Program, 2017](#)) will be based on the protein-creatinine ratio or 24-hour urinary protein result, if available. For subjects  $\geq 18$  years of age, if the subject has 4+ proteinuria by dipstick, a 24-hour urinary protein result is required to confirm Grade 3 proteinuria.

##### Management of Proteinuria

- Management of lenvatinib administration will be based on the grade of proteinuria according to [Table 1](#).
- In the event of nephrotic syndrome, lenvatinib must be discontinued.

##### Detection and Confirmation

- Perform urine dipstick testing per the Schedule of Assessments ([Table 5](#) and [Table 6](#))
- For subjects  $\geq 18$  years of age, a 24-hour urine collection initiated as soon as possible and at least within 72 hours (or an immediate spot urine protein-to-creatinine ratio [UPCR] test) AND for subjects  $< 18$  years of age, an immediate spot UPCR test, and if possible, a 24-hour urine collection (initiated as soon as possible and at least within 72 hours) is required in the following situations:
  - The first (initial) occurrence of  $\geq 2+$  proteinuria on urine dipstick while on lenvatinib
  - A subsequent increase in severity of urine dipstick proteinuria occurring on the same lenvatinib dose level
  - When there has been a lenvatinib dose reduction and at the new dose level the urine protein dipstick result is  $\geq 2+$
- For subjects  $\geq 18$  years of age, a 24-hour urine collection (initiated as soon as possible and at least within 72 hours) to verify the grade of proteinuria is required when UPCR is  $\geq 2.4$ .

##### Monitoring

- Urine dipstick testing for subjects with proteinuria  $\geq 2+$  should be performed on Day 15 (or more frequently as clinically indicated) until the results have been 1+ or negative for 2 consecutive treatment cycles.

- Proteinuria monitoring can be performed at the local laboratory or investigator site, but must be managed by the site physician.

#### 8.4.1.1.5 MANAGEMENT OF HEPATOTOXICITY

Regular monitoring of liver function tests (ALT, AST, bilirubin levels) should be conducted as detailed in the Schedule of Assessments ([Table 5](#) and [Table 6](#)) and as clinically indicated. If signs/symptoms indicating liver injury occur, instructions contained in the table for dose reduction and interruptions of the protocol should be followed (see [Table 1](#)). Appropriate supportive care should be provided together with close monitoring. If hepatic failure occurs the study drug must be discontinued.

#### 8.4.1.1.6 MANAGEMENT OF THROMBOEMBOLIC EVENTS

Subjects should be advised to pay attention to symptoms suggestive of venous thromboembolic events which include acute onset of shortness of breath, dyspnea, chest pain, cough, hemoptysis, tachypnea, tachycardia, cyanosis, deep vein thrombosis signs including lower-extremity swelling, redness and warmth to touch or tenderness. In case any of these symptoms appear, subjects should be instructed to report such symptoms promptly to the treating physician. If a thromboembolic event is confirmed, instructions contained in the table for dose reduction and interruptions of the protocol should be followed (see [Table 1](#)). Appropriate supportive care should be provided together with close monitoring. If a subject experiences a Grade 3 or a life-threatening (Grade 4) thromboembolic reaction, including pulmonary embolism, study drug must be discontinued.

Arterial thromboembolic events (eg, new onset, worsening, or unstable angina, myocardial infarction, transient ischemic attack, and cerebrovascular accident) of any grade require study drug discontinuation.

#### 8.4.1.1.7 MANAGEMENT OF HYPOCALCEMIA

Serum calcium should be monitored monthly per the Schedule of Assessments ([Table 5](#) and [Table 6](#)). Corrected serum calcium should be used to assess the grade of hypocalcemia per CTCAE v5.0, using the following formula:

$$\text{Corrected calcium} = ([4 - \text{serum albumin in g/dL}] \times 0.8 + \text{serum calcium})$$

The formula is not applicable when serum albumin concentration is normal (>4 g/dL); in such situations, the total (uncorrected) serum calcium should be used instead.

Hypocalcemia should be treated per institutional guidelines (eg, using appropriate calcium, magnesium, and Vitamin D supplementation) until resolution.

#### 8.4.1.1.8 MANAGEMENT OF GASTROINTESTINAL SYMPTOMS AND ACUTE ABDOMINAL PAIN

Initial management of acute abdominal pain in these study subjects should be focused on treating the underlying cause where possible, ensuring appropriate hydration/rehydration, and symptomatic pain improvement consistent with subject's age and in accordance to local and

institutional standards of care. Appropriate supportive care should be provided together with close monitoring.

For adverse events of abdominal pain believed related to lenvatinib or more specific adverse events believed related to lenvatinib that result in the symptom of abdominal pain, follow instructions contained in [Table 1](#) regarding study treatment dose reduction and interruption. For Grade 4 adverse events that result in abdominal pain, study drug must be discontinued.

Gastrointestinal symptoms including diarrhea should be managed by providing symptomatic treatment. If the symptoms persist (eg, diarrhea for more than 10 days), dose modification guidelines should be followed as per [Table 1](#). Gastrointestinal symptoms should be monitored closely and evaluated using CT, contrast-enhanced MRI, ultrasound, or other diagnostic imaging if clinically indicated, at the investigator's discretion.

Lenvatinib should be discontinued in any subject who develops gastrointestinal perforation of any grade or Grade  $\geq 4$  fistula.

#### 8.4.1.1.9 MANAGEMENT OF HEMORRHAGE

Dose modification guidelines as per [Table 1](#) for lenvatinib related adverse events should be followed for the management of hemorrhage. Either resume lenvatinib at a reduced dose or discontinue lenvatinib, depending on the severity and persistence of hemorrhage.

#### 8.4.1.2 Management of Ifosfamide-Etoposide Associated Toxicity

Blood counts should be closely monitored during and prior to the next cycle of chemotherapy. Chemotherapy-associated myelosuppression should be managed by granulocyte-colony stimulating factor (G-CSF). It is recommended that pegylated G-CSF or G-CSF be administered at least 24 to 72 hours after completion of ifosfamide-etoposide chemotherapy; use of G-CSF is recommended until white blood cell (WBC) counts are  $\geq 1 \times 10^9/L$ . Guidelines for dose modification for ifosfamide and etoposide associated toxicities are provided in the [Table 2](#) below.

Details of ifosfamide and etoposide dose interruption and reduction as well as management of toxicity can be found in the Summary of Product Characteristics (SmPC), and may be followed as per local and institutional guidelines. The SmPC will be provided to the study sites in the Investigator and Pharmacy files in the relevant local language. For additional information investigators may refer to the SmPC or Euramos-1 protocol (ISRCTN67613327 EudraCT no. 2004-000242-20).

**Table 2 Criteria for Dose Modification of Chemotherapy Dose**

Toxicity	Grade	Action
Neutropenia	Grade 4	Monitor ANC counts every 3 days until resolved to <Grade 3
Febrile neutropenia	Grade 4	Reduce the next dose of ifosfamide and etoposide by 20%
Mucositis	Repeated grade 3 or Grade 4	Reduce etoposide by 20%
Renal Toxicity	Serum creatinine is 1.5 – 3 × ULN maximum serum creatinine for age and gender	Interrupt ifosfamide and etoposide for 1 week
Hematuria	>50 RBC/ high power field (hpf)	Interrupt ifosfamide for 1 week
Neurological Toxicity	≥ Grade 2	Interrupt and reduce ifosfamide and etoposide each by 20% of the previous dose. After 2 dose reductions, subject must discontinue the chemotherapy drugs, but if benefiting, can continue on single-agent lenvatinib at the investigator's discretion

ANC = absolute neutrophil count, RBC = red blood cell, ULN = upper limit normal.

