### 8.3.2 Exclusion Criteria

Subjects who meet any of the following criteria will be excluded from this study:

1. Any active infection or infectious illness unless fully recovered prior to Cycle 1 Day 1 (ie, no longer requiring systemic treatment).
2. Subjects with central nervous system metastases are not eligible, unless they have completed local therapy (eg, whole brain radiation therapy, surgery or radiosurgery) and have discontinued the use of corticosteroids for this indication for at least 2 weeks before Cycle 1 Day 1.
3. Active second malignancy within 2 years prior to enrollment ([in addition to osteosarcoma], but not including definitively treated superficial melanoma, carcinoma-in-situ, basal or squamous cell carcinoma of the skin).
4. Any medical or other condition that in the opinion of the investigator(s) would preclude the subject's participation in a clinical study.
5. Has had major surgery within 3 weeks prior to Cycle 1 Day 1. Note: Adequate wound healing after major surgery must be assessed clinically, independent of time elapsed for eligibility.
6. Known hypersensitivity to any component(s) of the study drugs (lenvatinib, ifosfamide, and etoposide, or their ingredients).
7. Currently receiving any investigational drug or device in another clinical study or within 28 days prior to Cycle 1 Day 1.
8. A clinically significant ECG abnormality, including a marked baseline prolonged QT or QTc interval (eg, a repeated demonstration of a QTc interval >480 msec).
9. Gastrointestinal malabsorption, gastrointestinal anastomosis, or any other condition that in the opinion of the investigator might affect the absorption of lenvatinib.
10. Pre-existing Grade  $\geq 3$  gastrointestinal or non-gastrointestinal fistula.
11. Gastrointestinal bleeding or active hemoptysis (bright red blood of at least  $\frac{1}{2}$  teaspoon) within 3 weeks prior to Cycle 1 Day 1.
12. Radiographic evidence of intratumoral cavitation, encasement, or invasion of a major blood vessel. Additionally, the degree of proximity to major blood vessels should be considered for exclusion because of the potential risk of severe hemorrhage associated with tumor shrinkage/necrosis after lenvatinib therapy.
13. History of ifosfamide-related Grade  $\geq 3$  nephrotoxicity or encephalopathy.

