#### 8.4.2.2 Comparator Drug

##### Cytotoxic Chemotherapy: Ifosfamide and Etoposide

The cytotoxic chemotherapy drugs (used in combination with lenvatinib) in this study will be ifosfamide and etoposide. These chemotherapy drugs will be provided by the sponsor or sourced by the clinical sites. The administration procedure should follow the approved prescribing information in each country/region. The chemotherapy regimen schedule and dosing details are provided below.

The chemotherapy regimen schedule will consist of ifosfamide 3000 mg/m^2/day IV infusion over 30 minutes for 3 consecutive days (Day 1 to Day 3 of each cycle) and etoposide 100 mg/m^2/day IV infusion for 3 consecutive days (Day 1 to Day 3 of each cycle). Chemotherapy administration should be accompanied by vigorous hydration and administration of mesna according to the institutional guidelines. Each chemotherapy cycle will be 21 days for a total of 5 cycles.

Pegylated G-CSF or G-CSF will be administered at least 24 to 72 hours after completion of ifosfamide-etoposide chemotherapy until WBC counts are  $\geq 1 \times 10^9/L$  or at the investigator's discretion.

Anti-emetic or any other prophylaxis should be administered in accordance with institutional guidelines.

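### Table 2 gives no renal action above 3 times the age/sex creatinine maximum and a single rule for all neurological toxicity from Grade 2 up, so Arm B has no explicit protocol stop for the most severe events

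*Protocol*

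**What the plan says.** Protocol Section 8.4.1.2 introduces Table 2 in soft terms: "Guidelines for dose modification for ifosfamide and etoposide associated toxicities are provided" there. It also points to the Summary of Product Characteristics (SmPC) for details of interruption, reduction and toxicity management, which "may be followed as per local and institutional guidelines", and to the Euramos-1 protocol for further information.

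Two of the six rows of Table 2 matter here.

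- Renal toxicity. The trigger is "Serum creatinine is 1.5 – 3 × ULN maximum serum creatinine for age and gender". The action is to interrupt ifosfamide and etoposide for one week.
- Neurological toxicity. The trigger is Grade 2 or higher. The action is "Interrupt and reduce ifosfamide and etoposide each by 20% of the previous dose", followed by the only mandatory stop in the table: "After 2 dose reductions, subject must discontinue the chemotherapy drugs".

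The document contains the protocol text in two versions, and Table 2 reads the same in both.

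Exclusion criterion 13 (Section 8.3.2) begins "History of ifosfamide-related Grade" and goes on to bar entry for prior nephrotoxicity or encephalopathy of Grade 3 or above.

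**The concern.** A dose-modification table should become stricter, or at least stay defined, as toxicity worsens. Here the renal rule ends at 3 times the maximum, so the milder event has an instruction and the worse one has none. The neurological rule does not end, but it answers a life-threatening event in the same way as a moderate one.

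Subjects are aged 2 to 25 years, every subject in both arms is assigned ifosfamide and etoposide, and about 70 sites are planned. Without a stated threshold, the handling of the worst renal and neurological events rests on each site's judgment and on documents outside the protocol. What is at stake is patient safety and consistent handling across sites, not the trial's inference.

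**Working it through.** The point rests on no sample size, power or alpha figure, so there is no figure in the plan to reproduce. The check is a reading of the rows with simple arithmetic.

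**Step 1: the renal row.** Inputs are the multipliers 1.5 and 3 from Table 2 and the age/sex creatinine maxima in inclusion criterion 10 (Section 8.3.1). I assume that Table 2 refers to those maxima. The band runs from 1.5 × maximum to 3 × maximum.

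| Age and sex | Maximum (mg/dL) | Band with an action (mg/dL) | No action listed above |
|---|---|---|---|
| 2 to <6 y | 0.8 | 1.2 to 2.4 | 2.4 |
| 6 to <10 y | 1.0 | 1.5 to 3.0 | 3.0 |
| 10 to <13 y | 1.2 | 1.8 to 3.6 | 3.6 |
| 13 to <16 y, male | 1.5 | 2.25 to 4.5 | 4.5 |
| 13 to <16 y, female | 1.4 | 2.1 to 4.2 | 4.2 |
| ≥16 y, male | 1.7 | 2.55 to 5.1 | 5.1 |
| ≥16 y, female | 1.4 | 2.1 to 4.2 | 4.2 |

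Within the band, the interruption is a fixed week, and the row states no creatinine level for restarting.

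**Step 2: the neurological row.** Starting doses are ifosfamide 3000 and etoposide 100 mg/m²/day (Section 8.4.1). Each step is previous dose × 0.8.

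- First reduction: 3000 × 0.8 = 2400; 100 × 0.8 = 80.
- Second reduction: 2400 × 0.8 = 1920; 80 × 0.8 = 64.

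The steps are the same whether the event is Grade 2, 3 or 4. After a first Grade 4 event the row permits 2400/80 once the interruption is over, and it foresees a further step to 1920/64 before the mandatory stop.

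**Step 3: count.** Table 2 has six rows: neutropenia, febrile neutropenia, mucositis, renal, hematuria and neurological. Rows with an action for creatinine above 3 times the maximum: 0 of 6. Rows naming discontinuation of chemotherapy: 1 of 6, and only after two reductions.

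**Step 4: does another provision close the gap?**

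- Table 1 ends treatment at Grade 4, but Section 8.4.1.1 confines it to lenvatinib-related toxicity. Arm B receives no lenvatinib.
- Section 8.5.1.4.3 sends clinically significant laboratory abnormalities to Table 1, not Table 2. It also requires retesting at least every 3 days for chemistry toxicity of Grade 3 or above. That is monitoring, not a dosing rule.
- Section 8.3.3 ends treatment for unacceptable toxicity, which is not defined, and lets the investigator stop at any time for safety.
- Section 8.1.2.1 lets chemotherapy that was precluded on Day 1 restart after recovery, at the investigator's discretion. Recovery is not quantified.
- Section 8.4.2.2 states: "The administration procedure should follow the approved prescribing information in each country/region". That concerns how the drugs are given. The SmPC wording on toxicity in Section 8.4.1.2 is permissive.

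Each of these allows a stop. None sets a threshold for chemotherapy-related toxicity.

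**The case against.** The best case against is that the protocol delegates this detail on purpose. Table 2 is offered as guidance, the SmPC is supplied to every site in the local language, and Euramos-1 is named as a further source. Those documents are not at hand and may contain exactly the missing stops. The investigator may end treatment for safety at any time, and restarting depends on recovery. In Arm A, a Grade 4 event judged lenvatinib-related stops treatment under Table 1. All of this stands, and it limits the point to what the protocol itself states. That sites would in fact act differently is a risk, not something shown.

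Four stronger readings are tempting and are not supported.

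- A reader might infer that Table 2 orders re-treatment at 2400/80 after a Grade 4 event. It does not. Interruption comes first, and the reduced dose applies only if the investigator restarts.
- A reader might infer that silence above 3 times the maximum allows dosing to continue. Nothing in the protocol directs treatment at that level.
- A reader might infer that Table 2 contradicts exclusion criterion 13. That criterion governs entry and sets no rule on study. It shows only which ifosfamide events the sponsor considers serious enough to rule out enrolment.
- A reader might infer from the mucositis trigger, "Repeated grade 3 or Grade 4", that the table grades its response by severity elsewhere. That row gives one action for both situations, so it sets a threshold for acting and is no precedent.

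**Conclusion.** The point holds in this limited form, and it should be fixed. Table 2 states no renal action above 3 times the age/sex maximum, and its neurological row does not distinguish Grade 4 from Grade 2. In Arm B, and in Arm A for events not attributed to lenvatinib, the protocol gives no explicit stop for a first event at the severe end of either toxicity. Discretion, the undefined limit on toxicity and the outside sources mitigate this without replacing a rule.

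The effect is on safety only. Alpha, power and the primary analysis are unaffected. The number of subjects concerned cannot be derived from the document. The conclusion rests on reading Table 2 literally and on the assumption that its creatinine limits refer to the maxima in inclusion criterion 10. It makes no claim about what the SmPC or Euramos-1 say.

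**What to change.** Amend two rows of Table 2.

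1. Renal row, open-ended. At 1.5 times the age/sex maximum or above, hold ifosfamide and etoposide for at least one week and until creatinine is below 1.5 times. Above 3 times, discontinue ifosfamide unless the sponsor agrees to a restart.
2. Neurological row, split. Grade 2, and Grade 3 other than encephalopathy, keep the current rule. Grade 4 chemotherapy-related toxicity, and ifosfamide encephalopathy of Grade 3 or above (for consistency with exclusion criterion 13), lead to permanent discontinuation of ifosfamide.

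Since this separates the two drugs, each amended row should also say whether etoposide may continue. The thresholds are proposals that the documents do not supply, and the sponsor's clinical team should confirm them.

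The cost is a protocol amendment and no additional subjects. A few subjects in either arm may stop or delay ifosfamide earlier, and some will need repeat creatinine tests before restarting. Retesting at least every 3 days is already required for chemistry toxicity of Grade 3 or above.

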#### 8.4.2 Identity of Investigational Product(s)

Lenvatinib will be supplied by the sponsor in labeled containers. The sponsor will package lenvatinib as open-label supplies. Lenvatinib will be provided to the sites as #4 size hydroxypropyl methylcellulose (HPMC) capsules in 3 strengths differentiated by color (iron oxide red and iron oxide yellow); 1-mg capsule (yellowish red cap and white body, containing 1 mg E7080 anhydrous free base), 4 mg capsule (yellowish-red cap and body, containing 4 mg E7080 anhydrous free base); and 10 mg capsule (yellowish-red cap with yellow body, containing 10 mg E7080 anhydrous free base). Excipients of the E7080 formulation will be calcium carbonate, mannitol, microcrystalline cellulose, hydroxypropylcellulose, low-substituted hydroxypropylcellulose, talc, hypromellose, titanium dioxide, iron oxide yellow, and iron oxide red. Lenvatinib capsules may be suspended in water or apple juice for children unable to swallow capsules. [Appendix 4](#) provides instructions for the preparation of the lenvatinib suspension.

##### 8.4.2.1 Chemical Name of E7080

- Test drug code: E7080
- Generic name: lenvatinib
- Chemical name: 4-[3-Chloro-4-(*N*-cyclopropylureido)phenoxy]-7-methoxyquinoine-6-carboxamide methanesulfonate
- Molecular formula: C21H19ClN4O4•CH4O3S
- Molecular weight: 522.96

#### 8.4.2.2 Comparator Drug

##### Cytotoxic Chemotherapy: Ifosfamide and Etoposide

The cytotoxic chemotherapy drugs (used in combination with lenvatinib) in this study will be ifosfamide and etoposide. These chemotherapy drugs will be provided by the sponsor or sourced by the clinical sites. The administration procedure should follow the approved prescribing information in each country/region. The chemotherapy regimen schedule and dosing details are provided below.

The chemotherapy regimen schedule will consist of ifosfamide 3000 mg/m^2/day IV infusion over 30 minutes for 3 consecutive days (Day 1 to Day 3 of each cycle) and etoposide 100 mg/m^2/day IV infusion for 3 consecutive days (Day 1 to Day 3 of each cycle). Chemotherapy administration should be accompanied by vigorous hydration and administration of mesna according to the institutional guidelines. Each chemotherapy cycle will be 21 days for a total of 5 cycles.

Pegylated G-CSF or G-CSF will be administered at least 24 to 72 hours after completion of ifosfamide-etoposide chemotherapy until WBC counts are  $\geq 1 \times 10^9/L$  or at the investigator's discretion.

Anti-emetic or any other prophylaxis should be administered in accordance with institutional guidelines.

#### 8.4.2.3 Labeling for Study Drug

Lenvatinib and the combination chemotherapy drugs, ifosfamide and etoposide, where supplied by the sponsor will be labeled in accordance with text that is in full regulatory compliance with each participating country and is translated into the required language(s) for each of those countries.

The following information will be provided (but not limited to):

- For clinical trial use only
- Name and address of the sponsor
- Chemical name / drug identifier
- Lot number/Batch number
- Storage conditions, expiration date if necessary

